6.5 Pre-specified Subgroup Analysis

We will investigate treatment effects across the following subgroups of clinical interest as follows: key subgroups age-group (8+ or younger) and initial dislocation status and initial duration of immobilisation. The purpose of subgroup analyses is to investigate if the estimated treatment effects are relatively consistent across subgroup and for this extent will be viewed as exploratory. None of the included subgroups are based on post-randomisation patient characteristics or events [15].

If there are too few participants in any subgroup (<=15) or one treatment arm of a subgroup (<=5), the analysis for that subgroup will not be conducted. Consistency of effects will be undertaken on the ITT population for the primary estimand. Treatment effects for subgroups will be derived by introducing an interaction term of treatment with the covariate representing the clinical grouping of interest in the main model for the primary estimand. Interactions will be examined in separate models for each clinical grouping of interest. If the clinical grouping is measured in a way that gives rise to a continuous variable, the interaction term will include the variable on the continuous scale for testing treatment effect modification by the characteristic of interest. Treatment differences will be then summarised and reported for changes over high-density areas of the distribution of such covariates i.e. 25%, 50% and the 75% centiles. Age groupings will be used here as these age groupings also represent parental help when responding to PROMIS self-report. The estimated treatment difference and confidence intervals will be reported and presented in forest plots.

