This technique involves immobilisation of the elbow to rest the elbow at around 90 degrees of flexion. The immobilisation device (i.e. cast/splint/bandage etc) is not applied with the intention of directly opposing the bone fragments, and therefore the bone fragments will not align perfectly. In this pragmatic trial the duration and method of immobilisation will be left to the discretion of the treating surgeon as per their usual technique, and will be worn as per the standard practice of the treating surgeon. Subsequently, the elbow will be allowed to mobilise as pain allows under the direction of the clinical team. Fixed immobilisation in a cast should not be used for more than 4 weeks post randomisation.

7.4.3 Rehabilitation;

In this pragmatic trial, any rehabilitation input, including a formal referral to physiotherapy, will be left to the discretion of the treating clinicians. However, a record of any rehabilitation input (type of input and number of additional appointments) together with a record of any other investigations/ interventions will be requested as part of the 4-week, 6-week, 3-month, 6-month, and 12-month follow-up datasets from both patients and clinical teams.

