Subgroups analyses will be undertaken with the aim of exploring the consistency of treatment effects across important baseline characteristics. These include age-groups (8+ or younger), initial immobilisation duration and dislocation status will be explored using treatment by subgroup interactions [15]. Forest plots with 95% confidence interval will be used to present the subgroup analysis results. Secondary clinical outcomes and patient reported outcomes will be similarly analysed using mixed effects regression, using logistic regression for binary data and linear regression for continuous data.

Any subsequent changes in this plan are strongly discouraged. If any changes to this SAP are implemented these will be documented in an updated version of this SAP. Documentation of any such changes will include the rationale for the changes, and when and by whom these were agreed.

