5.5 Treatment Compliance with Details of Intervention

The intervention groups in this trial are operative fixation or non-operative treatment of the medial epicondyle fracture of the elbow in children. As this is a one-off intervention, compliance is defined by the proportion of participants for each allocation that receive the treatment they were randomised to. The numbers and percentages of participants receiving each treatment are summarised, as well as those who did not receive the allocated treatment. Reasons are given in the cases where the participants did not receive the allocated treatment (Table 8).

Table 8: Compliance with allocated intervention

| Treatment Received | Operativ | e fixation | Non-operative treatment | |
|---|----------|------------|----------------------------|---|
| | n | % | n | % |
| Allocated Treatment | | | | |
| Other | | | | |
| Reasons for not receiving allocated treatment | | | | |
| Clinical decision | | | | |
| Child/Parent decision | | | | |
| Lack of equipment | | | | |
| Administrative error | | | | |
| Other | | | | |

Details of treatment received are summarised in Table 9.

Table 9: Information about Intervention Received

| | n | % |
|--|---|---|
| Operative Fixation: | | |
| Screws | | |
| Cannulated screws | | |
| Solid screws | | |
| Wires | | |
| Buried | | |
| Unburied | | |
| Other | | |
| Non-Surgical treatment: | | |
| Above elbow full cast | | |
| Above elbow back slab | | |
| Other splint | | |
| Bandage | | |
| Other | | |
| Post-Intervention Instructions: | | |
| Cast off at X weeks | | |
| Operative Fixation | | |
| Non-Surgical treatment | | |
| Immediate mobilisation as tolerated, with physiotherapy | | |
| Operative Fixation | | |
| Non-Surgical treatment | | |
| Immediate mobilisation as tolerated, without physiotherapy | | |
| Operative Fixation | | |
| Non-Surgical treatment | | |
| Rest until X weeks | | |
| Operative Fixation | | |
| Non-Surgical treatment | | |
| Other | | |
| Operative Fixation | | |
| Non-Surgical treatment | | |

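### Immobilisation duration is listed as a baseline subgroup, but the documents place it after randomisation and within each treatment, so its subgroup effects are open to bias

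*SAP*

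**What the plan says.** SAP 6.5 names "key subgroups age-group (8+ or younger) and initial dislocation status and initial duration of immobilisation" as the groupings of interest. For the method it says: "Treatment effects for subgroups will be derived by introducing an interaction term of treatment with the covariate representing the clinical grouping of interest". A grouping measured on a continuous scale enters as continuous, with treatment differences reported at its 25%, 50% and 75% centiles and shown in forest plots. The section assures the reader that "None of the included subgroups are based on post-randomisation patient characteristics or events", and says the analyses "for this extent will be viewed as exploratory".

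SAP 3.7 gives the aim as "exploring the consistency of treatment effects across important baseline characteristics" and continues: "These include age-groups (8+ or younger), initial immobilisation duration and dislocation status".

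On how immobilisation comes about, Protocol 7.4.2 says of the non-operative arm that "the duration and method of immobilisation will be left to the discretion of the treating surgeon". Under Protocol 7.4.1, the sling, plaster, splint or bandage goes on once the operation is finished, and mobilisation follows the surgeon's ordinary practice. SAP Table 9 records "Cast off at X weeks" under its post-intervention instructions, split by treatment.

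**The concern.** A subgroup analysis in a randomised trial is protected by randomisation only if the grouping variable was fixed before allocation. In that case the two arms within a stratum differ only by chance. A variable that treatment can change does not have this property. Children immobilised for three weeks after surgery may differ in prognosis from children immobilised for three weeks without it, so their comparison is observational.

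Duration also has a different role in each arm. It is the allocated treatment itself in one and aftercare in the other, so even without confounding it is hard to read as a patient characteristic that modifies the effect of surgery.

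At stake is one row or panel of a forest plot. The SAP's assurance invites the reader to take it as a randomised comparison, and an apparent pattern by duration could be read as a finding about immobilisation.

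**Working it through.** **Step 1: timing, from the text.**

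| Question | What the documents say | Where |
|---|---|---|
| When is the child randomised? | After consent, with details logged before treatment | Protocol 7.3.4, 7.3.5 |
| What is immobilisation in the non-operative arm? | The allocated treatment, with duration chosen by the surgeon | Protocol 7.4.2 |
| What is it in the operative arm? | Applied at the end of surgery, with mobilisation by the surgeon's practice | Protocol 7.4.1 |
| From when is the limit on cast time counted? | Randomisation, in both arms | Protocol 7.4.1, 7.4.2 |
| Where does the SAP tabulate it? | Table 9, after intervention, by treatment | SAP 5.5 |
| Is it a baseline item? | No; absent from Tables 5, 6 and 7 | SAP 5.3 |

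Age and dislocation at presentation, the other two subgroups, are genuine baseline variables. The conflict concerns this one only.

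**Step 2: the sample size used below.** SAP 3.3 gives 133 evaluable per arm (4 points, SD 10, two-sided 5%, 90% power). The normal approximation is 2 × (1.960 + 1.282)² × 10² / 4² = 131.3, so 132 per arm. With the noncentral t, power is 0.8993 at 132 and 0.9015 at 133, which reproduces 133. Then 133 / 0.8 = 166.25, so 167 per arm and 334 in total. The plan's figures reproduce, and 266 evaluable children are used here.

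**Step 3: what bias could look like.** Everything about duration and severity below is assumed. Let unmeasured severity cost b PROMIS points per SD. In each arm let duration have mean m, SD s and correlation r with severity (N non-operative, S surgery). Treatment has the same effect in every child, so there is no true interaction.

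- Spurious interaction per week = b × (rN/sN − rS/sS).
- If b × r/s equals k in both arms, the interaction is 0, but the effect at every duration is shifted by k × (mS − mN).
- Standard error of the interaction ≈ 10 × √[(1/133) × (1/sN² + 1/sS²)].

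Take b = 3, rN = 0.5, rS = 0, s = 0.6 weeks, mN = 3 and mS = 1.5. The interaction is 3 × 0.5/0.6 = 2.5 points per week. The standard error is 10 × √[2/(133 × 0.36)] = 2.04, so z = 1.22. The rejection rate is Φ(1.22 − 1.96) + Φ(−1.22 − 1.96) ≈ 0.23. Simulation of 2,000 trials also gives 23%.

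Other simulated scenarios; unless stated, b = 3, s = 0.6 and the means are as above:

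| Assumption | Interaction test rejects | Effect estimates |
|---|---|---|
| Duration unrelated to severity | about 5% | no bias |
| r = 0.5 in both arms, equal means | about 5% | no bias |
| r = 0.5 in both arms, surgery 1.5 weeks shorter | about 5% | shifted by about −3.8 at every centile (2.5 × −1.5 = −3.75) |
| rN = 0.2, rS = 0 | about 8% | – |
| rN = 0.5, rS = 0.3 | about 8% | – |
| b = 1.5, rN = 0.5, rS = 0 | 9.5% | – |
| rN = 0.3, rS = 0 | 11% | – |
| rN = 0.5, rS = 0, s = 1.0 | 22% | slope 1.5 points per week |

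A harsher set (3,000 trials) gives duration a mean of 3 weeks plus 0.5 weeks per SD of severity plus noise of SD 0.5, capped at 4 weeks.

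- Severity driving duration in the non-operative arm only: 31% rejection at b = 3, and 68–70% at b = 5. With b = 5, a true effect of +4 and surgery shortening duration by 1.5 weeks, the centile estimates are about −4.0, −0.5 and +4.2.
- Severity acting equally in both arms, b = 5, surgery 1.5 weeks shorter, true effect +4: rejection 5–6%, with centile estimates of about −3.8, −3.6 and −3.5. That is a shift of about 7.5 points and a reversed sign.

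**The case against.** Four points can be made for the plan.

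1. **The bias is not certain.** A reader might infer that the interaction test is biased as such. The documents do not support that. It needs duration to relate to prognosis differently in the two arms, and neither arm's description ties duration to severity. Several scenarios above keep the test at about 5%. This stands, so open to bias is the right wording. It does not clear the subgroup-specific effects, which can be shifted even when the test keeps its size.

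2. **No single figure can be defended.** A reader might quote 23% or 70% as the false-positive rate. Both depend wholly on assumed inputs, and the points-per-week slope also depends on the SD of duration, which no document gives. This stands. The figures are a range over the scenarios tried and do not estimate what will happen in this trial.

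3. **Initial may mean before randomisation.** Injuries up to two weeks old are eligible (Protocol 7.3.1), so splinting before allocation is possible and would be a true baseline variable. But no passage defines the term that way and no baseline table holds such an item. The reading cannot be excluded, yet it still requires a change to the SAP.

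4. **The analysis is exploratory.** SAP 6.5 says so. This stands and limits the severity. It does not justify keeping an assurance that the protocol contradicts.

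**Conclusion.** The point holds as an internal contradiction with a consequence for analysis. On the documents' own description, immobilisation duration is decided after randomisation by the treating surgeon and belongs to each treatment. SAP 3.7 and 6.5 present it as a baseline grouping. The effects by duration are open to bias, as is the interaction test where duration relates to prognosis differently by arm.

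The conclusion about timing rests on the text alone. The size rests on assumptions: false-positive rates from about 5% to about 70%, and shifts in the subgroup effects from none to more than the 4-point target difference.

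A reader might also infer that the main result is threatened. It is not: the primary estimand, primary model, sample size and other two subgroups are untouched. This should be fixed, but it is not critical.

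**What to change.** Remove immobilisation duration from the interaction and forest-plot analyses in SAP 3.7 and 6.5, and report it descriptively by arm as treatment received, as Table 9 already provides. The sentence on post-randomisation subgroups in 6.5 is then correct.

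If a pre-randomisation measure was intended, define it as such, state how it is recorded, and add it to the baseline table. Replacing it with another baseline subgroup is optional; Table 6 already holds candidates such as dominant-arm injury or mechanism of injury.

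The cost is an updated SAP version with the reason recorded, as SAP 3.7 requires for any change, and the loss of one exploratory analysis. Removing the variable changes no data collection, sample size or clinical management. The change should be made before any unblinded analysis.

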Broken bones of the elbow are common in children. Doctors have varying opinions about the best treatment for one particular type of elbow break, called a 'medial epicondyle fracture'. Some surgeons argue that these breaks should be treated with surgery to fix the bone with wires or screws, whilst others argue that treating the bone in a cast will give just as good results, without the risks and scars associated with surgery. The research to now is of poor quality and has results supporting both arguments. This means that the treatment that children receive is dependent on the beliefs and understanding of the surgeon, rather than proper science. Perhaps unsurprisingly, approximately half of children are treated with surgery, and half with a cast. High-quality research is urgently needed to answer this question.

What is the question being asked?

In children with this elbow injury (medial epicondyle fracture), does treatment with surgery result in better arm function after 1 year than treatment without surgery?

What sort of study is it?

The study is called a trial, which is the best method to compare treatments and the best way to get a proper answer. A computer will decide whether a child does or doesn't get surgery – the decision is made between the treatments at random.

How many children will be involved?

Children with this injury are usually around 10/11 years old, though anyone between 7 and 15 years can participate. It is hoped that 334 children will participate over a two year period from more than 35 hospitals in the United Kingdom, New Zealand and Australia. This number is calculated based on previous scientific research to ensure that the study is large enough to reach a firm conclusion.

What will families be asked?

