The PROMIS Upper Extremity Score has convergent validity with other tests used in the assessment of arm function in children with congenital limb abnormalities¹⁴, as well as with physiological tests of upper limb function (Grip Strength and Pinch Strength r>0.6 p<0.05). In the congenital limb population the PROMIS test was also the only tool without ceiling effects (when using the computer adaptive test but not a short form). The PROMIS Upper Extremity Score for Children appears to be the best tool to assess functional recovery in this group of patients. There is now agreement from an international group planning multicentre paediatric orthopaedic trials (IMPACCT), that the PROMIS Upper Extremity Tool is the preferred outcome to assess upper limb function in children. Within the SCIENCE trial, the lowest age of participating children is 7-years old. We are aware that self-reported PROMIS measures are generally used from 8-years-old, however outcome experts, including the developers of PROMIS, have advised us to use a single version of the questionnaire. Given this, we will collect self-reported function amongst all age children within the trial.

The secondary outcome measures in this trial are:

Sports/ Performing Arts Module of DASH¹⁵. This is a tool for recording details of sports and performing arts participation relating to upper extremity function. Clinicians and children have both indicated that sports participation must be considered within the analysis. DASH S/PA Module, is distinct from the more general DASH tool that lacks face validity amongst children. Although the DASH S/PA Module was not specifically developed in children, we have worked with our group of patient representatives to ensure that the tool is appropriate for use in children. There was universal agreement amongst patients (i.e. those present at an 'Elbow Study Day' that we held at Chester Zoo

in England and members of the NIHR Young Persons Advisory Group) that DASH S/PA Module has appropriate language to be used amongst children who are able to comprehend other self-reported questionnaires. The DASH S/PA Module therefore has face validity amongst the target population.

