7.3 Methodology

7.3.1 Screening and Eligibility

Patients will be eligible for this study if:

- There is radiographic evidence of a displaced medial epicondyle fracture of the Humerus, with fracture displacement determined by the surgeon as per their usual clinical practice.
- They are aged between 7 and 15 years old inclusive.

Patients will be excluded from participation in this study if:

• The injury is more than two weeks old.

- There is incarceration of the medial epicondyle fragment within the elbow joint.
- The injury is part of a complex elbow fracture (i.e. fracture extending into the joint).
- There are other fractured bones elsewhere in the body, in addition to the elbow injury.
- The elbow, if dislocated, is unable to be realigned into a satisfactory position in the emergency department.
- There is evidence that the patient and/or parent/guardian would be unable to adhere to trial procedures or complete follow-up, such as insufficient English language comprehension, developmental delay or a developmental abnormality or no access by parents to the internet.

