2. BACKGROUND AND OBJECTIVES

The management of fractures of the medial epicondyle is a controversial issue in paediatric fracture care [3]. These fractures typically occur in children around 10-12 years old [4], with or without dislocation of the elbow joint. The debate for clinicians is whether to realign and hold the bone fragments with operative fixation, or whether to allow the fragments to heal in their current position without surgery by resting the elbow in a cast.

Observational studies have demonstrated support for both operative and non-operative treatment strategies, generating uncertainty amongst surgeons. Two published systematic reviews have demonstrated disagreement in the management of this injury [4, 5]. One systematic review concluded that nonsurgical treatment offers excellent functional results equivalent to surgical treatment [5]. The other concludes that surgical fixation should be strongly considered to achieve union of the bone fragments thereby maximising elbow stability for an increasingly athletic child population [4]. To add further to the debate, a widely used 'evidence-based review' textbook has recently advocated against surgery, citing increased long-term pain and stiffness compared to non-operative treatment [6].

Much of the controversy has arisen because there have been no prospective studies evaluating the treatment of these fractures. Current literature has serious methodological limitations, especially with regard to inconsistent follow-up, no standardisation to treatment approaches, infrequent use of patient reported outcomes, and selection bias for operative fixation [6]. There has also been a lack of agreement on how to record successful outcomes; with radiographic union of the fracture fragments being the most commonly used outcome, and pain or function being infrequently recorded, although there is known to be poor correlation between radiographic union and functional outcomes [5]. The uncertainty within the literature has resulted in considerable variation in clinical practice. There is an increasing tendency toward surgery, which has been particularly driven by US literature identifying the athletic demands of children and adolescents, and the expectations of early mobilisation and return to sport [3-7].

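### The age subgroup compares 7-year-olds with ages 8–15: it may be dropped and has little power if kept, so the SAP should add its default continuous-age test

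*SAP*

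**What the plan says.** SAP section 6.5 names three exploratory subgroup factors: "key subgroups age-group (8+ or younger) and initial dislocation status and initial duration of immobilisation". SAP section 3.7 gives the same age cut. Protocol section 7.3.1 sets the age limits: "They are aged between 7 and 15 years old inclusive". The younger group is therefore age 7 alone, one of nine eligible years of age.

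Three further rules in SAP section 6.5 bear on this:

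- **Minimum size.** The rule begins "If there are too few participants in any subgroup (<=15". It applies equally when one arm of the subgroup has 5 or fewer. The analysis is then not done.
- **Continuous modifiers.** For a modifier measured continuously, "the interaction term will include the variable on the continuous scale for testing treatment effect modification". Treatment differences are then reported at the 25th, 50th and 75th centiles.
- **Exception for age.** The text then says: "Age groupings will be used here as these age groupings also represent parental help when responding to PROMIS self-report".

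Age is listed as continuous in SAP Table 6 and is already a fixed effect in the primary model (SAP section 6.2). On who reports, Protocol section 6.3 says that "we will collect self-reported function amongst all age children within the trial". It also notes that PROMIS self-report is generally used from age 8. On typical age, SAP section 2 says "These fractures typically occur in children around 10-12 years old", and the protocol's lay summary says "Children with this injury are usually around 10/11 years old, though anyone between 7 and 15 years can participate". Neither document gives an age SD or distribution.

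**The concern.** The cut falls at the bottom edge of the eligible range, below the ages at which the injury is typical. The younger group could be too small for the SAP's own size rule. If it passes, its interval will be wide. The older group is nearly the whole trial and pools ages 8 to 15, so any trend with age inside that span cannot be seen.

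The forest plot may therefore have no age row. Or it may have one whose 7-year-old interval is so wide that a reader takes it, wrongly, as evidence of consistency. Age is one of only three planned subgroup factors. The SAP discourages later changes, and a continuous-age test introduced after the results are known would carry less weight than one planned now.

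**Working it through.** **The plan's own figure.** Inputs from SAP section 3.3: difference 4, SD 10, two-sided 5%, power 90%.

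- n per arm = 2 × (1.960 + 1.282)² × 10² / 4² = 131.4, so 132 by the normal approximation.
- The plan's 133 per arm gives 90.4% power (normal) or 90.1% (t-test).
- 133 / 0.8 = 166.25, so 167 per arm and 334 in all. The plan's figures reproduce.

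**Chance of being dropped.** At least 16 seven-year-olds are needed: 16/334 = 4.8% of those randomised, or 16/266 = 6.0% of those expected to be evaluable. The age distributions below are assumptions: normal, truncated to 7.0 to under 16.0, with a uniform spread for reference. The chance of being dropped is an exact binomial calculation (total ≤15, or either arm ≤5 under 1:1 allocation).

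| Assumed age | Share aged 7 | Count of 334 / 266 | Chance dropped, 334 / 266 |
|---|---|---|---|
| mean 10, SD 2.5 | 11.0% | 37 / 29 | <1% / <1% |
| mean 10, SD 3 | 11.5% | 38 / 30 | <1% / <1% |
| mean 10.5, SD 2 | 6.9% | 23 / 18 | 8% / 32% |
| mean 11, SD 2 | 4.5% | 15 / 12 | 60% / 87% |
| mean 11, SD 2.5 | 6.5% | 22 / 17 | 11% / 39% |
| mean 11.5, SD 2 | 2.9% | 10 / 8 | 97% / >99% |
| uniform | 11.1% | 37 / 30 | <1% / <1% |

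**Precision if kept.** For a 12-month comparison with 1:1 arms, the interaction SE = SD × √(4/n₇ + 4/(N − n₇)). With SD 10 and N = 334:

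- n₇ = 16: SE = 10 × √(4/16 + 4/318) = 5.12. Power for 4 points is 12%, and the interaction detectable with 80% power is 14.4 points. The 95% half-width among 7-year-olds is 1.96 × 10 × √(4/16) = 9.8 points.
- n₇ = 37: SE = 10 × √(4/37 + 4/297) = 3.49. Power is 21%, the detectable interaction 9.8 points, and the half-width 6.4 points.

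The SAP expects an SD below 10 but gives no figure. At an assumed SD of 7, power with 16 to 37 seven-year-olds is 20% to 37%. At an assumed SD of 5 it is 35% to 63%.

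**Split against continuous age, on the same trend.** The SE of the continuous slope is 2 × 10 / (√N × age SD), with the age SD taken after truncation. Worked case, mean 11 and SD 2 with N = 266: truncated age SD 1.84, interquartile range 2.61 years, and mean ages of the two groups 3.67 years apart.

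- *Trend A, 4 points across the interquartile range.* Slope 4/2.61 = 1.53 per year; SE 20/(√266 × 1.84) = 0.67; power 63%. The same slope makes the groups differ by 1.53 × 3.67 = 5.6 points; with 12.1 seven-year-olds the SE is 5.89; power 16%.
- *Trend B, 4 points between 7 and 8+.* Slope 4/3.67 = 1.09 per year; power 37% for continuous age and 10% for the split.

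Power from N = 266 to N = 334:

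| Assumed age | A: continuous | A: split | B: continuous | B: split |
|---|---|---|---|---|
| mean 10, SD 2.5 | 60–70% | 21–25% | 50–59% | 18–21% |
| mean 10, SD 3 | 57–67% | 20–24% | 51–60% | 18–21% |
| mean 10.5, SD 2 | 63–73% | 19–22% | 42–51% | 13–15% |
| mean 11, SD 2 | 63–73% | 16–19% | 37–45% | 10–12% |
| mean 11, SD 2.5 | 59–69% | 17–21% | 42–50% | 13–15% |
| mean 11.5, SD 2 | 63–73% | 13–15% | 32–39% | 8–9% |

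Where the expected count is 15 or fewer, the split's power is notional, because the size rule would probably remove it. These figures ignore any precision gained from repeated measures; that simplification applies to both tests.

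**The case against.** The strongest reply is that the SAP asks a different question. Its only stated reason for grouping age is help from parents, and 8 is the usual lower limit for PROMIS self-report. A check at that boundary targets the one age at which self-report is used outside its usual range. A linear age term would not isolate age 7. This stands, and it is why the 7 v 8+ comparison should be kept.

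Three stronger readings are tempting, and the documents do not support them.

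- *The subgroup will be dropped.* A reader might infer this from the typical age of 10–12. Without an age distribution it cannot be shown. The denominator also matters: section 6.5 uses the ITT population and the primary model uses all available data on randomised participants, which points towards 334 rather than 266.
- *The SAP contradicts itself.* The sentence on age directly follows the continuous-scale rule and gives its reason, so it is an explicit exception. It may even cover only how results are summarised. Nor does self-report at every age conflict with it, since the SAP speaks of help with self-report and not of a different reporter. Neither document shows, though, that help stops at 8.
- *Continuous age makes the question well powered.* Setting 12% for a 4-point gap between 7 and 8+ beside the power for 4 points across the interquartile range compares two different slopes. On a common trend the advantage remains but is smaller, and under trend B continuous age reaches only 32–60%.

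Low power is also general for subgroups here: at SD 10 and N = 266, even an even split has interaction SE = 10 × √(4/133 + 4/133) = 2.45 and about 37% power for 4 points.

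**Conclusion.** The point holds as a cheap improvement of low severity. It is certain from the documents that the split is age 7 against ages 8–15. Whether it would be dropped is unknown, with a chance from under 1% to about 100% across the assumed distributions. If it is kept, it is uninformative at the planning SD of 10: about 12% power for a 4-point interaction with 16 seven-year-olds and about 21% with 37. Continuous age is the stronger test in all six truncated-normal cases: 57–73% against 13–25% under trend A, and 32–60% against 8–21% under trend B. The comparison assumes a linear trend, the age distributions listed and an outcome SD of 10. A smaller SD would help both tests. The subgroup analyses are exploratory, and no primary or secondary conclusion depends on this one.

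**What to change.** In SAP section 6.5, name a treatment-by-continuous-age interaction in the primary model as the test of effect modification by age. Report treatment effects at the 25th, 50th and 75th centiles of age, as the SAP's general rule already provides. Keep 7 v 8+ as a descriptive check on reporting help, and say that this is its purpose. Carry the same wording into section 3.7.

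The cost is a sentence or two in the SAP and one more exploratory analysis. No new data are needed, since age is already a covariate. The drawback is the assumed linear age trend, which should be stated with the result.
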